16 HOW SUPPLIED/STORAGE AND HANDLING

RAYALDEE is supplied as 30 mcg calcifediol in blue, oval extended-release capsules, imprinted O:

Bottles of 30 [NDC 70301-1001-1]

Bottles of 60 [NDC 70301-1001-2]

Store at 20-25°C (68-77°F); excursions permitted to 15-30°C (59-86°F) [see USP Controlled Room Temperature].

17 PATIENT COUNSELING INFORMATION

- Tell patients to take RAYALDEE at bedtime and to swallow the capsules whole.
- Inform patients if they miss a dose, to take RAYALDEE at the next scheduled time. Do not take an extra dose to make up for the missed dose.
- Inform patients that they will need routine monitoring of laboratory parameters such as calcium, iPTH and total 25-hydroxyvitamin D while taking RAYALDEE.

- Advise patients to contact a health care provider if they develop symptoms of elevated calcium (e.g., feeling tired, having difficulty thinking clearly, loss of appetite, nausea, vomiting, constipation, increased thirst, increased urination or weight loss).
- Advise patients to inform their physician of all use of medications, including prescription and nonprescription drugs, supplements and herbal preparations, and of any changes in medical condition. Patients should also be advised to inform their physicians, when receiving a newly prescribed medication, that they are taking RAYALDEE.
- Inform lactating women about the need to monitor infants exposed to RAYALDEE through breast milk for signs of hypercalcemia to include seizures, vomiting, constipation and weight loss [see Use in Specific Populations (8.2)].

RAYALDEE® is a registered trademark of EirGen Pharma Ltd.

Patent: https://www.opko.com/what-we-do/our-research/patents

Manufactured for: OPKO Pharmaceuticals, LLC [name]

© 2021 OPKO Pharmaceuticals, LLC All rights reserved.

APPENDIX 3. PATIENT REPORTED OUTCOMES

Participant ID:	
-----------------	--

Participant Initials: Date: 1

FLU-PRO Plus®

People experience viral respiratory tract infections in different ways. We would like to know about the symptoms you have been experiencing during the past 24 hours. For each symptom, please mark one box
under the response that best matches your experience. if you did not have that symptom in the past 24 hours. Mark

What time is it? _____AM / PM (please circle)

Please rate the extent to which you had each symptom during the past 24 hours.

Runny or dripping nose		
Congested or stuffy nose		
Sinus pressure		
Scratchy or itchy throat		
Sore or painful throat		
Difficulty swallowing		
Teary or watery eyes		
Sore or painful eyes		
Eyes sensitive to light		
Trouble breathing		
Chest congestion		
Chest tightness		
Dry or hacking cough		
Wet or loose cough		
Felt nauseous (feeling like you wanted to throw-up)	1	
Stomach ache		
Felt dizzy		
Head congestion		
Headache		
© 2014 Leidos Biomedical	August 20, 2015 FLU-PRO Version 2.0	Page 1 of 2

Page 1 of 2

CTAP101 | CTAP101-CL-2014 | CTAP101-CL-2014 Protocol VV-TMF-183735 | Version 8.0 dated 16 Nov 2021

Protocol CTAP101-CL-2014 CTAP101 (calcifediol) Extended-release Capsules

Participant ID:

Participant Initials: ____Date: / /

Please rate the extent to which you had each symptom during the past 24 hours.

Lack of appetite
Sleeping more than usual
Body aches or pains
Weak or tired
Chills or shivering
Felt cold
Felt hot
Sweating

In the past 24 hours, how often have you had any of the following symptoms?

How	w many times did you nit?
How	w many times did you have rrhea?

In the past 24 hours, did you have any of the following symptoms?

Loss of smell	
Loss of taste	

© 2014 Leidos	August 20, 2015 FLU-PRO Version 2.0		
Biomedical		Page 2 of 2	
Research, Inc.	Research Tool in Development:		

OPKO Pharmaceutcials, LLC Page 81 of 82

FLU-PRO^c GLOBAL ADDITIONAL DAILY DIARY ITEMS

Items to be asked in daily diary for the length of the study along with the FLU-PRO symptom items.

1. Overall, how severe were your infection symptoms today? (Please select one response only)

2. Overall, how were your infection symptoms today compared to yesterday? (Please select one response only)

3. How much did your infection symptoms interfere with your usual activities today? (Please select one response only)

4. Have you returned to your usual activities today?

5. In general, how would you rate your physical health today? (Please select one response only)

6. Have you returned to your usual health today?

1 Copyright © 2014, 2015, 2016, 2017 Leidos Biomedical Research, Inc. All Rights Reserved.

Protocol CTAP101-CL-2014	
CTAP101 (calcifediol) Extended-release Caps	sules

ICF Informed Consent Form ITT Intent-to-treat ICH International Council for Harmonisation IRB/EC Institutional Review Board/Ethics Committee PP per-protocol PTH parathyroid hormone SAE serious adverse event SARS-CoV-2 severe acute respiratory syndrome coronavirus 2 SD standard deviation SOC system organ class TEAE treatment-emergent adverse events

1 INTRODUCTION/BACKGROUND

This statistical analysis plan (SAP) describes data analysis specifications for the CTAP101-CL-2014 protocol (version 8.0) entitled, "A Randomized, Double-Blind Placebo-Controlled Study to Evaluate the Safety and Efficacy of Rayaldee (calcifediol) Extended-release Capsules to Treat Symptomatic Patients Infected with SARS-CoV-2 (REsCue)". The SAP follows the International Council on Harmonisation (ICH) Guidelines E3 and E9. All statistical analyses will be performed using SAS®, Version 9.4 or higher. In cases in which the analyses in this SAP differ from those in the study protocol, the analyses in the SAP supersede those in the protocol.

2 STUDY OBJECTIVES

2.1 Primary Objectives

The primary objectives of this study are to compare the effects of Rayaldee (CTAP101 Capsules) versus placebo treatment in patients with mild to moderate COVID-19 on the:

- Attainment of serum total 25-hydroxyvitamin D (25D) levels at or above 50 ng/mL by Day 14; and,
- Severity and duration of disease as evidenced by five COVID-19 symptoms (trouble breathing, chest congestion, dry or hacking cough, body aches and pains, and chills and shivering) using the FLU-PRO Plus[©] questionnaire as the data collection tool.

2.2 Estimand

The study treatment estimand is the difference between 28 days of Rayaldee and placebo treatment in adult patients with confirmed SARS-CoV-2 infection who have unresolved symptoms of mild to moderate COVID-19 in (a) the attainment of serum total 25D levels \geq 50 ng/mL as assessed at treatment Day 14, and (b) the number of days to resolution of five symptoms (trouble breathing, chest congestion, dry or hacking cough, body aches and pains, and chills and shivering), as measured by the FLU-PRO Plus[©] questionnaire with resolution defined as the first aggregate symptom score of \leq 5 which is maintained for a minimum of three consecutive days.

2.3 Secondary Objectives

The secondary objectives of the study are to compare the effects of Rayaldee (CTAP101 Capsules) versus placebo treatment on:

- The number of days to resolution of five symptoms (trouble breathing, chest congestion, dry or hacking cough, body aches and pains, and chills and shivering), as measured by the FLU-PRO Plus[©] questionnaire, with resolution defined as the first aggregate symptom score of ≤5 which is maintained for a minimum of three consecutive days, with no individual symptom score >1;
- Resolution, defined as the first score of ≤5 which is maintained for a minimum of three consecutive days (without subsequent relapse), for the aggregate five COVID-19 symptoms (trouble breathing, chest congestion, dry or hacking cough, body aches and pains, and chills and shivering) and for each individual symptom, defined as a score of 0 or 1, as measured by the FLU-PRO Plus[©] questionnaire as of Day 10;
- Incidence of emergency room/urgent care visits;
- Incidence of oxygen saturation below 94% (or requirement for oxygen supplementation);
- Incidence and duration of hospitalizations;
- Incidence of requirement for mechanical ventilation;
- Mortality rate (as incidence);
- Severity and duration of COVID-19 illness as evidenced by quality-of-life measures using the FLU-PRO Plus[©] questionnaire; and,

• Clinical course of COVID-19 as a function of serum 25D concentrations of <50 ng/mL, 50 to 100 ng/mL and >100 ng/mL at Days 7, 14, 21 and 28, defined as the proportion of subjects in each treatment group with a total score of ≤5 for the selected five COVID-19 symptoms (trouble breathing, chest congestion, dry or hacking cough, body aches and pains, and chills and shivering) using the FLU-PRO Plus[©] questionnaire.

3 STUDY DESIGN

3.1 Overview

This is a phase 2 multi-center, randomized, double-blind placebo-controlled study to evaluate the safety and efficacy of Rayaldee (CTAP101 Capsules) to treat adult subjects with unresolved symptoms of mild to moderate COVID-19 who test positive for SARS-CoV-2 via any FDA-approved diagnostic test. Subjects will be randomized to receive either oral Rayaldee (CTAP101 Capsules) or matching placebo. Approximately 80 subjects will be randomized in a blinded manner to each of the Rayaldee (CTAP101 Capsules) and placebo treatment groups, for a total of approximately 160 subjects.

3.2 Treatment Administration

Subjects will receive a loading dose (900 mcg Rayaldee or matching placebo) split into three equal doses of 300 mcg each administered on Days 1, 2 and 3, followed by 24 daily maintenance doses (60 mcg on Days 4 to 27) administered at bedtime after fasting for at least 3 hours following dinner.

3.3 Sample Size Calculation

Primary outcome #1 (attainment of serum 25D levels at ≥50 ng/mL): Assuming that no more than 25% of the control group will achieve an increase in serum 25D to ≥50 ng/mL by Day 28 versus greater than 75% in the CTAP101 Capsules group, a sample size of 19 per group will provide 90% power at one-sided alpha of 0.025 based on a Chi-square test of the two groups.

Primary outcome #2 (severity of illness by selected five COVID-19 symptoms): A sample size of 80 per group (total of 160) is planned. This will provide greater than 80% power at one-sided alpha of 0.025 based on a log rank test assuming 50% of subjects in the control group and 70% of the CTAP101 Capsules group will have achieved resolution of symptoms by Day 28. This is based on an expected hazard ratio (of achieving resolution) of 1.74.

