5.3.4 Method of Assigning Subjects to Treatment Groups

After signing the informed consent form (ICF), prior to any study-related activities, each subject will be assigned a 5 digit identification number and will retain this number throughout the study. The 5 digit identification number (SS-EEE) will consist of a 2-digit study site number (SS) and a 3-digit consecutive enrollment number (EEE). Should a subject be withdrawn from the study, that subject's 5 digit identification number will not be reassigned.

Approximately 250 subjects will be screened to enroll approximately 160 subjects who meet screening criteria. The IRT will provide study treatment group assignments for these subjects using a computer-generated randomization code. Subjects will be randomized in a blinded manner into 1 of 2 treatment groups (approximately 80 subjects per group) in a 1:1 ratio of Rayaldee (CTAP101 Capsules) or placebo, respectively.

5.4 **Prior and Concomitant Therapy**

Subjects should be willing to limit the use of vitD therapy and vitD supplements except for normally fortified food products (eg, milk) during the course of the 6-week study other than the study drug. Standard of care medications for CKD (VitD, calcitriol, paricalcitol and doxercalciferol) should be suspended during the treatment period. Excluded therapies at enrollment include thiazide diuretics, 1α -hydroxylated vitD analogs (calcitriol, paricalcitol and doxercalciferol) and vitD supplements (cholecalciferol and ergocalciferol). Current treatment with cytochrome P450 inhibitors, such as ketoconazole, atazanavir, clarithromycin, indinavir, itraconazole, nefazodone, nelfinavir, ritonavir, saquinavir, telithromycin or voriconazole, which may inhibit enzymes involved in vitD metabolism and may alter serum levels of calcifediol, must be evaluated by the investigator and may be a reason for exclusion from the study. Medications that could impair the absorption of fat-soluble nutrients and dietary calcium supplements providing more than 0.5 g of elemental calcium are not allowed.

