9.4 Determination of Sample Size

Primary outcome #1 (attainment of serum 25D levels at \geq 50 ng/mL): Assuming that no more than 25% of the control group will achieve an increase in serum 25D to \geq 50 ng/mL by Day 28 versus greater than 75% in the CTAP101 Capsules group, a sample size of 19 per group will provide 90% power at alpha 0.025 one sided for a Chi-square test of the two groups.

Primary outcome #2 (severity of illness by five symptoms): A sample size of 80 per group (total of 160) is planned. This will provide greater than 80% power at one sided alpha of 0.025 based on a log rank test assuming 50% of subjects in the control group and 70% of the CTAP101 Capsules group will have achieved resolution of symptoms by Day 28. This is based on an expected hazard ratio (of achieving resolution) of 1.74.

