- 2. The number of days to resolution of the selected five COVID-19 symptoms (trouble breathing, chest congestion, dry or hacking cough, body aches and pains, and chills and shivering), defined as a reduction in the aggregate symptom score recorded on Day 0 (prior to study drug initiation) by the FLU-PRO Plus[©] questionnaire to or below 5 for a minimum of three consecutive days. These five symptoms are part of the chest/respiratory and body/systemic domains of the FLU-PRO Plus[©] questionnaire for which average scores of ≥1.5 were required for each domain for inclusion in the study. Trouble breathing, chest congestion and dry or hacking cough are symptoms indicative of potentially inadequate oxygenation and an impending requirement for supplemental oxygen and hospitalization. Body aches and pains and chills and shivering are symptoms indicative of systemic inflammatory responses associated with active viral infection. Resolution of each of these five symptoms will be analyzed separately, as well, as secondary efficacy endpoints. An aggregate score for the primary efficacy endpoint related to the selected five COVID-19 symptoms is deemed appropriate in view of the observed heterogeneity in COVID-19 symptom profiles. Not all subjects experience the same symptoms or degree of symptom severity. For example, some subjects experience trouble breathing but are free of dry or

hacking cough. Others have no difficulty breathing but report chest congestion or coughing. This situation supports an argument against focusing on one or two symptoms, as a significant number of subjects may not have experienced those symptoms. It also supports an argument to use an aggregate score, since consideration of a larger number of symptoms makes the endpoint applicable to a larger number of subjects. Based on analysis of blinded data obtained from the study, more than 92% of subjects who received at least one dose of study drug had an aggregate symptom score higher than 5 at baseline (Day 0). The main reason why a few subjects do not have an aggregate baseline score higher than 5 is that they get well rather quickly, even before starting study drug. Such subjects will be excluded from the FAS.

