6.10 Efficacy Analyses

6.10.1 Primary Efficacy Endpoints

The two primary efficacy endpoints will be tested hierarchically to maintain an overall one-sided alpha level of 0.025. Therefore, the test of resolution of symptoms based on the aggregate FLU-PRO Plus[©] symptom score will be performed only if the attainment of serum 25D levels \geq 50 ng/mL at Day 14 is significant at <0.025.

The first primary efficacy endpoint, attainment of serum 25D levels at ≥50 ng/mL, will be assessed with a Chi-square statistic at Day 14. The serum 25D levels will also be compared between treatment groups at Days 7, 21 and 28 with a Chi-square statistic.

The second primary efficacy endpoint is the number of days to resolution of symptoms, defined as a reduction in the aggregate FLU-PRO Plus[©] score for the selected five COVID-19 symptoms recorded on Day 0 (prior to study drug initiation) to or below 5 for a minimum of three consecutive days. The time to resolution is defined as the number of days from Day 1 (study drug initiation) to the first day of achieving the aggregate ≤5 score for a minimum of three consecutive days, provided that no score greater than 5 is recorded between the two qualifying scores. Resolution will be determined by the first two successive qualifying scores which span a minimum of three consecutive days. For clarity, resolution will be considered as having been achieved if two successive aggregate scores of ≤5 are recorded on the first day of this occurrence and on a subsequent day that is at least two days (but not more than 5 days) later even if no score has been recorded between the two days. Missing symptom score values will be handled as described in Section 6.2. The number of days to resolution will be analyzed with a Cox proportional hazards model with covariates (baseline aggregate FLU-PRO Plus[©] score for the selected five COVID-19 symptoms, baseline serum 25D, and body weight).

As a sensitivity analysis of the resolution of symptoms, a tipping point approach will be used starting with the analysis in which scores are available for three consecutive days, with no missing interval, followed by increasing numbers of missing days in the up to five-day interval, that is, 1, 2 and 3 missing days between the two consecutive qualifying scores.

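### Greater than 80% power for time to symptom resolution does not follow from the plan's own Day 28 inputs: 80 per group gives about 75–77%, and about 72–74% in the full analysis set at 92% retention

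*SAP*

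**What the plan says.** SAP 3.3, Protocol 9.4 and the protocol synopsis carry the same calculation for the second primary endpoint. On size: "A sample size of 80 per group (total of 160) is planned". On power: "This will provide greater than 80% power at one-sided alpha of 0.025 based on a log rank test assuming 50% of subjects", where the 50% is the placebo rate. For the active arm, the assumption is that "70% of the CTAP101 Capsules group will have achieved resolution of symptoms by Day 28". On effect: "This is based on an expected hazard ratio (of achieving resolution) of 1.74". Allocation is "in a 1:1 ratio of Rayaldee (CTAP101 Capsules) or placebo" (Protocol 5.3.4), and the two primary endpoints are "tested hierarchically to maintain an overall one-sided alpha level of 0.025" (SAP 6.10.1).

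None of the three passages gives an expected number of events, a censoring day, or an allowance for drop-out or exclusions. Protocol 6.9 says that withdrawn subjects will not be replaced.

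The symptom-resolution tables in SAP 8.1 (14.2.1.5 to 14.2.1.8) are for the FAS and per-protocol populations only. SAP 5.2 reports from blinded data that "more than 92% of subjects who received at least one dose of study drug had an aggregate symptom score higher than 5 at baseline" and says that the rest are left out of the FAS.

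**The concern.** Every input to a log-rank power calculation is given: test, one-sided alpha, allocation, sample size, the two resolution proportions and the hazard ratio. The figure can therefore be checked, and it comes out below the claim. The FAS exclusion lowers it further, and the SAP reports that exclusion without carrying it into the power statement.

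Protocol 3.4.1 defines a successful outcome as one-sided significance on this endpoint. The stated power tells a reader how often a true effect of the assumed size would be missed. The plan implies less than 20%. Its own inputs imply about 23–25%, or 26–28% in the FAS at 92% retention. A non-significant result would then carry less weight against the assumed effect than the plan suggests.

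**Working it through.** **Inputs.** 80 per group, 1:1; 50% (control) and 70% (active) resolved by Day 28; one-sided alpha 0.025 (z = 1.960); log-rank test. All are from SAP 3.3 and Protocol 9.4, with allocation from Protocol 5.3.4.

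**Step 1: hazard ratio.** Under proportional hazards, HR = ln(1 − 0.70) / ln(1 − 0.50) = ln(0.30) / ln(0.50) = 1.737. The plan's 1.74 reproduces.

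**Step 2: expected events by Day 28.** 80 × 0.50 + 80 × 0.70 = 96.

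**Step 3: power with 96 events.**
- Schoenfeld: Φ(√(96/4) × ln 1.737 − 1.960) = Φ(4.899 × 0.552 − 1.960) = Φ(0.745) = 77.2%.
- Freedman: Φ(√96 × (0.737/2.737) − 1.960) = Φ(9.798 × 0.2693 − 1.960) = Φ(0.678) = 75.1%.
- Using 1.74 in place of 1.737 gives 77.4% and 75.4%.
- Lachin–Foulkes 75.6%; normal approximation on the log hazard ratio 76.0%; Lakatos 76.9–77.0%.
- Simulated log-rank test (40,000 runs, exponential times, censored at Day 28): 77.3%.
- For comparison, a chi-square test of 50% against 70%: 73.7%.

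None reaches 80%.

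**Step 4: what 80% power needs.**
- Schoenfeld: 4 × (1.960 + 0.842)² / 0.552² gives 103 events. At 1.2 events per pair, 103 / 1.2 = 86 per group (172 in total).
- Freedman: (1.960 + 0.842)² / (0.737/2.737)² gives 109 events, or 108 with HR 1.74. That is 90–91 per group (180–182 in total).

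**Step 5: the analysed set.** At 92% retention, 0.92 × 80 = 73.6 per group (about 147 in total), and 73.6 × 1.2 = 88.3 events.

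| Method | 80 per group, 96 events | FAS at 92%, 88.3 events |
|---|---|---|
| Schoenfeld | 77.2% | 73.7% |
| Freedman | 75.1% | 71.6% |
| Lachin–Foulkes | 75.6% | 72.2% |
| Lakatos | 76.9–77.0% | 73.4–73.5% |
| Simulated log-rank | 77.3% | 73.6% (74 and 73 subjects) |

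**Step 6: inputs that would give more than 80%.**
- One-sided alpha of 0.05: 84–86%. The plan uses 0.025.
- 70% resolved in both arms (112 events): 81–83%. This contradicts the assumed 50%.
- Constant hazards continued to Day 42: the unresolved proportions become 0.50^1.5 = 0.354 and 0.30^1.5 = 0.164, so events are 80 × (2 − 0.354 − 0.164) = 118.6 and power is 83.4% (Freedman) to 85.2% (Schoenfeld). In the FAS, 109.1 events give 80.3% to 82.2%.

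**Step 7: the other primary endpoint.** 19 per group for 25% against 75% gives 90.2% power, so that calculation reproduces. The discrepancy is confined to the symptom endpoint.

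**The case against.** The strongest reply is that Day 28 only fixes the assumed rates and is not a stated follow-up limit. The endpoint definition has no cut-off at Day 28. Subjects stay in the study to Day 42 (Protocol 3.5), and the diary is kept daily over that time (Protocol 7.10 and 7.11). If those later resolutions count and the hazards stay constant, power exceeds 80% even in the FAS. This stands in part: the plan gives no censoring day, so a Day 42 analysis is possible. It does not rescue the statement as written. The calculation names resolution by Day 28, and neither the later horizon nor the constant-hazard extrapolation appears in any sample-size passage.

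Four smaller points:
- The 92% is a floor, so the FAS figures are the low end for that exclusion. The excluded subjects mostly recovered before dosing, and the plan does not say which population the 50% and 70% describe. This stands: the FAS figure is approximate. The shortfall at the full 160 does not depend on it.
- Missing scores before resolution count as unresolved (SAP 6.2), so the assumed rates may already absorb some drop-out. That is possible, but the plan does not say so.
- The planned analysis is a Cox model with three baseline covariates, and adjustment may add power. The documents give nothing from which to quantify this, and the claim is expressly for a log-rank test.
- The gap is modest for a phase 2 trial, and a null result would also be read from the estimate and its precision. That is fair, but it does not make the stated figure correct.

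**Conclusion.** The concern holds. On the inputs the plan states, 80 per group gives about 75–77% power, 3 to 5 points short of 80%. In the FAS at the 92% floor it gives about 72–74%, 6 to 8 points short. Undosed subjects, and any drop-out the assumed rates do not already absorb, would lower it further.

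The Schoenfeld and Freedman figures at Day 28 rest on proportional hazards and the plan's two resolution proportions. Lachin–Foulkes, Lakatos and the simulation also assumed exponential times. The FAS figures assume that events fall in proportion to subjects. The claim is met only if resolutions to Day 42 count and hazards stay constant after Day 28, and the plan states neither.

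**What to change.** Correct the text in SAP 3.3, Protocol 9.4 and the synopsis in one of two ways:

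1. **Keep the Day 28 basis.** State 96 expected events and log-rank power of about 75–77% for 80 per group. Add that an FAS of about 147 subjects (92% retained) would have about 88 events and about 72–74% power.
2. **Use the Day 42 basis.** State that resolutions through Day 42 count in the analysis, give the censoring rule, and state the constant-hazard assumption. Expected events are then about 119 for all randomised subjects (83–85% power) and about 109 in the FAS (80–82%).

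Under either option, name the population to which the 50% and 70% apply, and say whether drop-out is allowed for.

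The cost is a few words in three places. No extra patients or visits are needed, and the test and alpha stay as they are. Under the first option the stated power becomes slightly less favourable. The second requires the sponsor to commit to an analysis horizon that the plan now leaves open.
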